#### **Specific Aim 2 - Detecting Treatment Effects on Molecular Mechanisms.**

The effect of the treatment on methylation and inflammation (HYPOTHESIS 2) will be analyzed with one 2 (**Treatment:** 8 weeks of MBRP vs. 8 weeks of RP) x 5 (**Time:** Baseline, 4, 8, 20, 32 weeks) mixed multivariate general linear model with methylation outcomes of DRD2, SLC6A3, and DBH and a second model with peripheral inflammation outcomes of IL-6, IL-8, and TNF $\alpha$ . The effect of the treatment on cue-elicited BOLD activation and network connectivity (HYPOTHESIS 3) will be analyzed with a 2-way multivariate analysis of variance (MANOVA; **Treatment:** 8 weeks of MBRP vs. 8 weeks of RP) with BOLD activation in the accumbens, caudate, putamen, and anterior cingulate regions as separate outcomes in the same analysis, and a second MANOVA with network connectivity

The image part with relationship ID rid9 was not found in the file.

in the RECN and LECN as the outcomes. Note, again, that FIML estimation will be used to allow full utilization of available data in an intent to treat framework. It is also possible that the treatments are equally effective on drinking outcomes, and thus we will not see a differential effect of treatment on the mediators. Yet it is still important to know whether levels of methylation or inflammation post-treatment have any impact on changes in

neurocognitive outcomes. Thus, the test of Specific Aim 3 is still critical, even in the case that both treatments are equally effective on both the mediators and drinking outcomes.

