### **Specific Aim 1.**

#### Comparing the effectiveness of MBRP (n=113) to RP (n=113).

- Hypothesis 1. It is hypothesized that MBRP will demonstrate superior effectiveness, as compared to RP, by reductions in heavy drinking days at the end of treatment (8 weeks) and longer term (20 and 32 weeks) decreases in liver function tests (8, 20, and 32 weeks).

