## ***MRI and Connectivity:***

### **MRI Data Collection (Baseline and Week 32).**

Before treatment begins and at the 6 month follow-up appointment (week 32), subjects will participate in an fMRI cue exposure session (Claus et al., 2011). Participants who are determined eligible to have an MRI scan will undergo a structural scan, using a Siemens 3T Trio, followed by a functional MRI scan that involves alcohol cue exposure. Our cue procedure is consistent with NIAAA guidelines and less risky than previous studies that have examined this mechanism in a sample receiving treatment (e.g., Myrick et al., 2008; Spagnolo et al., 2014; see protection of human subjects section). **Structural MRI (sMRI):** We will acquire a high-resolution protocol sufficient to permit accurate tissue classification and anatomical parcellation. For optimal contrast between gray matter (GM), white matter (WM) and cerebral spinal fluid (CSF) at 3T, we will use a multi-echo MPRAGE (MEMPR) sequence with the following parameters: TR/TE/TI = 2300/2.74/900 ms, flip angle = 8°, FOV = 256x256 mm, Slab thickness = 176 mm, Matrix = 256x256x176, Voxel size = 1x1x1 mm, Number of echos = 4, Pixel bandwidth = 650 Hz, Total scan time = 6 min. **Functional MRI (fMRI) – Cue-Elicited BOLD:** fMRI scans will be collected with single-shot full k-space echo-planar imaging (EPI) with ramp sampling correction using the intercommissural line (AC-PC) as a reference (TR: 2.0 s, TE: 27ms,  $\alpha$ : 70°, matrix size: 64 × 64, 32 slices, voxel size: 3 × 3 × 4 mm^3). Image-based higher order automatic shimming will be employed. FMRI data will be acquired with a 32-channel coil. Scanner instability and signal-to-noise ratio during fMRI scanning on a phantom will be monitored weekly throughout the project period. Automated analysis of scanner instability with the Weiskoff method is routinely performed. We have used our alcohol cue task successfully in over 600 individuals (Claus et al., 2011). It is reliable and well validated. The task compares the taste of an individual's favorite alcoholic beverage with a sweet, appetitive control taste (litchi juice). The task was designed to minimize movement by only administering 1 ml of each beverage through Teflon tubing that is attached to a computer controller gustometer, over each 24 second trial. It is important to note that the total amount of the alcoholic beverage is only 12 ml (less than a teaspoon). The task itself involves a block design with twelve pseudorandomly ordered alcohol and control trials that are presented in two consecutive runs. In order to examine whether the effects of MBRP differ from those of RP, we will calculate the signal change for alcohol minus the control condition in the precuneus, putamen, and anterior cingulate and use the signal in these regions of interest (ROIs) in the structural equation models (see analysis section).

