### ***Power Analysis:***

#### **Sample Size Requirements.**

Sample size was selected to permit analysis of the hypotheses at a two-tailed alpha of .05 and power level of at least .80 following Cohen (Cohen, 1988). G\*Power 3.0.3 (Erdfelder, Faul, & Buchner, 1996) was utilized for some power calculations, while Monte Carlo simulation strategies formed the basis of our power analysis for the mediational model ([name], Schmiege, & Broaddus, 2007; Mackinnon & Dwyer, 1993).

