### **Power for Specific Aim 2 - Detecting Treatment Effects on Putative Molecular Mechanisms.**

As reviewed above, the effect sizes for the impact of MBIs (and thus likely MBRP) on inflammatory biomarkers and epigenetic regulation ranged from moderate to large. Thus, for tests of the hypotheses under Specific Aim 2, that there will be treatment effects on both inflammatory markers and epigenetics, the effect sizes are in all cases larger than our estimated effects of treatment on outcomes. Thus, 226 participants are more than adequate for Hypothesis 2 of Specific Aim 2. In terms of Hypothesis 3 of Specific Aim 2, there are no data available to estimate the size of the direct effects of MBRP on cue-elicited BOLD activation or on network connectivity. With 226 participants, we will be able to detect a direct effect as small as  $d=.38$  (a small to moderate effect) on change in BOLD activation and network connectivity as a result of MBRP versus RP.

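### The Hypothesis 3 imaging MANOVA names only treatment as a factor, does not match the change outcome it is powered on, and makes no routine adjustment for the baseline scan

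*Combined protocol and SAP*

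**What the plan says.** Scans are taken twice. MRI Data Collection states: "Before treatment begins and at the 6 month follow-up appointment (week 32), subjects will participate in an fMRI cue exposure session". Resting State Connectivity gives the same two times.

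In the Data Analysis Plan, Specific Aim 2, the effect of treatment on BOLD and connectivity "will be analyzed with a 2-way multivariate analysis of variance". The parenthesis that follows lists treatment alone. The first model is described "with BOLD activation in the accumbens, caudate, putamen, and anterior cingulate regions as separate outcomes in the same analysis", and a second MANOVA takes connectivity in the two executive control networks. The Hypothesis 2 model in the same section, by contrast, is written out as treatment by five time points. The section adds that "FIML estimation will be used to allow full utilization of available data in an intent to treat framework".

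Power for Specific Aim 2 describes the same hypothesis as a direct effect "on change in BOLD activation and network connectivity as a result of MBRP versus RP". Specific Aim 3 also uses changes in these measures.

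Two general rules bear on the point. The Data Analysis Plan places FIML in Proc Mixed and EQS. Its pretest-equivalence paragraph brings in a baseline variable as covariate only if the arms differ on it after Bonferroni correction.

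**The concern.** A two-way analysis needs two factors, and one is given. The text can be read as a comparison of follow-up scans, a comparison of change scores, or a treatment-by-time analysis with time left out. These have different precision, and the plan does not choose between them. None of them includes routine adjustment for the baseline scan, and the pretest rule does not supply it, because that rule depends on an observed imbalance.

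The named method and the named estimator also do not fit. A conventional MANOVA discards anyone with an incomplete outcome vector. A participant who misses the second scan lacks every region at once. If only follow-up outcomes are modelled, even likelihood estimation then recovers nothing for that person. The documents foresee several routes to a missing second scan: 20% attrition, a negative pregnancy test required before it, a repeated option to opt out, and no MRI during remote operation.

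At stake are the precision of Hypothesis 3 and a clear statement of what it tests.

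**Working it through.** **Inputs from the documents**
- "two-tailed alpha of .05 and power level of at least .80" (Sample Size Requirements).
- 113 per arm (Specific Aim 1).
- "With 226 participants, we will be able to detect a direct effect as small as" d = .38 (Power for Specific Aim 2).
- 20% attrition (The impact of attrition): 113 × 0.8 = 90.4, taken as 90 per arm.

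**Assumed inputs**
- Scan-rescan correlation r = .3, .5 and .7. The only repeated-measures correlation in the documents, about .50, is stated for the Aim 1 drinking outcomes.
- The number scanned. Only MRI-eligible participants are scanned, and the count is not stated.

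**Step 1: the plan's own figure.** For a two-group comparison, power = Φ(d·√(n/2) − 1.96) = Φ(0.38 × √56.5 − 1.96) = Φ(0.896) = .81. The detectable d at 80% power is 2.80 × √(2/113) = .37. The stated .38 is thus reproduced as a plain two-group comparison of 113 with 113. It fits a follow-up-only comparison in follow-up SD units or a change comparison in change SD units, so it does not show which is meant. It includes no gain from baseline adjustment and assumes that all 226 have usable scans.

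**Step 2: variance of the arm contrast relative to follow-up only** (equal variances at both scans)
- Follow-up only: 1
- Change score: 2(1 − r)
- Baseline-adjusted: 1 − r²

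With two scans and complete data, the interaction in an unconstrained treatment-by-time model equals the difference in mean change, so it takes the change-score factor. Now 1 − r² is below 1 whenever r is not 0. Also 1 − r² = (1 − r)(1 + r), which is below 2(1 − r) whenever r is below 1. For r strictly between 0 and 1, adjustment therefore beats both alternatives.

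**Step 3: detectable d at 80% power, 90 per arm**, in follow-up SD units: 2.80 × √(2/90 × factor)

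| r | Follow-up only | Change score | Baseline-adjusted |
|---|---|---|---|
| .3 | .42 | .49 | .40 |
| .5 | .42 | .42 | .36 |
| .7 | .42 | .32 | .30 |

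**Step 4: power at d = .38 with r = .5** (t-based). With 113 per arm, power is .81 for follow-up only or change, and .91 adjusted. With 90 per arm it is .72 and .83.

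**Step 5: missing second scans.** In a simulation with 113 per arm, r = .5 and 20% of follow-up scans missing completely at random, the standard error was .151 for follow-up only, .149 for change and .130 baseline-adjusted.

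These are univariate illustrations. The planned tests are multivariate, with four BOLD outcomes and two connectivity outcomes, so their power also depends on correlations among outcomes.

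**The case against.** A reader might infer that the baseline scan is wasted. The documents do not support that. The power section and Specific Aim 3 both speak of change, and a change score uses the baseline scan. The two-way label itself suggests a second factor, and the preceding model is treatment by time, so an omitted time factor is at least as plausible as a follow-up-only test. What stands is that the analysis section does not say which, and does not match the power section.

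A reader might also infer that FIML cannot be used for this hypothesis. That goes too far. The plan names Proc Mixed and EQS, and a multi-outcome treatment contrast can be fitted by likelihood in either. The supportable point is that a conventional MANOVA does not provide FIML, and that FIML has nothing to recover for a wholly missed second scan unless the baseline scan is in the model.

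Three limits on the size also stand. If one reading is held fixed, the gain can be small: about .02 in d against follow-up only at r = .3, or against change at r = .7. The 90 per arm is not the number scanned. And Hypothesis 3 is not the primary outcome, which is heavy drinking days.

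**Conclusion.** The point holds as a gap in specification and a missed gain in precision; it is not a source of bias. The Hypothesis 3 test lacks a defined outcome and second factor, does not match the change outcome in its power statement, and names a method that in its conventional form does not give the stated handling of missing data. Whether follow-up only or change is meant, baseline adjustment is more efficient for any r strictly between 0 and 1. At r = .5 it cuts variance by 25%. Across r = .3 to .7 with 90 per arm, the detectable d is .40 to .30 adjusted, against .42 for follow-up only and .49 to .32 for change.

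The sizes rest on assumed correlations, equal variances at the two scans, a univariate formula and an assumed number scanned. The efficiency ordering does not depend on the values chosen for r or for the number scanned. This is a free improvement.

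**What to change.** Replace the two MANOVAs with likelihood-based multivariate mixed models in Proc Mixed, which the plan already names. Take both scans as outcomes, constrain baseline means to be equal across arms, and test the arm effect at the follow-up scan. Include framewise displacement as covariate in the connectivity model; Resting State Connectivity already plans this, but the Aim 2 analysis text omits it. Participants with only a baseline scan then stay in the likelihood, although they add limited information on the arm effect.

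ANCOVA of the follow-up value on arm and baseline value is a simpler alternative. It gains the precision but still omits those without a second scan.

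Align Power for Specific Aim 2 with the analysis text, stating the outcome, the number expected to have usable scans and the assumed scan-rescan correlation. Reconcile the time of the second scan before finalizing the model: MRI Data Collection, Resting State Connectivity and Follow-up Assessment II give week 32, while Specific Aim 3 and the MRI entry in the procedures table give week 8.

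The cost is a text edit. Both scans and the software are already planned.

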### **Specific Aim 3 - Mediational analyses.**

Mediational analyses based on structural equation modeling with latent variables will be used to examine the mechanisms by which MBRP has its effects on behavioral outcomes related to alcohol use and dependence (See Figure 4; HYPOTHESIS 4) (Baron & Kenny, 1986; [name] et al., 2007). Mediational analyses will utilize the methylation and inflammation data collected at 4 weeks, and changes in cue-elicited BOLD activation and network connectivity strength at 8 weeks as the mediators, and drinking outcome data collected at 20 weeks. The exogenous variable in the model is the contrast that compares MBRP to RP. Methylation, inflammation, and drinking outcomes are all conceptualized as latent variables, which means that they are not directly measured, but are rather inferred via the measurement of variables thought to be a consequence of the latent variable. Latent variables have advantages over measured variables in that they are more reliable and thus allow for higher power for the test of relationships between the underlying construct and other variables (Kline, 2010).

The model is then estimated in EQS, and both the fit of the model and the significance of the path coefficients are examined. If HYPOTHESIS 4 is supported, we will see significant paths from the treatment contrast to methylation and inflammation. Further, there will be significant paths from methylation to cue-elicited BOLD activation and from inflammation to network connectivity. Finally, we expect significant relationships between BOLD activation and network connectivity to drinking outcomes. Importantly, tests for the completeness of mediation of the treatment differences in drinking outcomes are employed through a one degree of freedom  $\chi^2$  test where a path directly from the treatment contrast to drinking outcomes is added to the model. A nonsignificant direct path and a nonsignificant change in  $\chi^2$  suggest that treatment effects on drinking outcomes were mediated through the series of molecular and brain-based mechanisms. A secondary test of mediation will utilize bootstrap methods to test the significance of, and confidence limits around, the mediated effect (Mackinnon & Dwyer, 1993). Similar mediational analyses have been widely used by Co-I [name] ([name] et al., 2007).

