## **Molecular Mechanisms Underlying Alcohol-Induced Adaptations in Reward and Control Circuitry.**

As described in Figure 1, emerging evidence suggests that molecular mechanisms such as epigenetic regulation and changes in immune system function, particularly inflammatory processes, are involved in the effects of alcohol on control and reward circuits. We will discuss the evidence for the immune system first, followed by the role of epigenetic regulation.

At first glance, the link between AUDs and immune processes may not be obvious. However, recent studies have suggested that perturbation of the immune system is a critical mechanism in the etiology of AUDs (for reviews see Mayfield, Ferguson, & Harris, 2013; Leclercq et al., 2012; Leclercq et al., 2014). More specifically, alcohol produces deleterious effects on peripheral and central immune signaling pathways, particularly through activation of lipopolysaccharide (LPS)-induced TLR4 signaling cascades that span the gut, liver, and brain, and coincide with the release of cytokines and other pro-inflammatory pathways in the brain (Fernandez-Lizarbe, Pascual, & Guerri, 2009). Repeated activation of pro-inflammatory pathways and microglia is

**Figure 1.** Summary of the rationale for the proposal. Chronic alcohol exposure leads to changes in the immune system via TLR4 mediated increases in cytokines and microglial activation, which in turn lead to damage to the executive control networks and diminished control. At the same time, alcohol exposure leads to epigenetic modification of key dopamine genes, leading to sensitized reward responding and craving. MBRP putatively reduces cytokine signaling and neuroinflammation and mitigates or reverses epigenetic changes, thereby restoring balance in the control and reward networks and reducing relapse after treatment. This research proposes to test these mechanisms and pathways.

associated with increased neuroinflammation and neural damage in frontal brain regions involved in executive function and control (Alfonso-Loeches et al., 2010; Guerri & Pascual, 2010). These neuroinflammatory processes have also been implicated in the etiology of a number of other neurodegenerative diseases as well as the deleterious effects of aging on cognitive function (Smith, Das, Ray, & Banik, 2012; Ownby, 2010; Lyman et al., 2014).

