While animal models have indicated that acute and chronic alcohol use is associated with increased levels of LPS circulating in the blood, there have also been studies in humans demonstrating that acute binge drinking releases LPS which in turn ligates TLR4 and activates the release of cytokines and inflammation. Specifically, a recent study in humans tested the effects of an acute binge episode on circulating LPS levels (Bala et al., 2014). The study estimated that the physiological dose of LPS after a binge episode was 100 pg/ml. As part of the study, peripheral blood mononuclear cells (PBMCs) were isolated from subjects and challenged ex-vivo with a 100 pg/ml dose of LPS. The study observed significant induction of cytokines (TNF $\alpha$ , IL-6, MCP1). Thus, these data are also consistent with the notion that the alcohol/LPS/TLR4/neuroinflammation pathway is a central mechanism in the etiology of AUDs.

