#### **Liver Function Panel Tests (Baseline, Week 8, 20, 32).**

As stated in the study background, LPS-induced pro-inflammatory cascades span the brain, gut, and liver (Fernandez-Lizarbe, Pascual, & Guerri, 2009). Additionally, enzyme levels detected in a liver function panel (LFT) can indicate possible liver damage and cirrhosis cause by alcohol abuse (Bellentani et al., 1997). We expect to see changes in liver function tests as a result of decreased alcohol consumption and pro-inflammatory markers associated with RP and MBRP therapy. The LFT will also provide an additional objective measure of alcohol consumption to supplement the self-report measures we will collect. To detect differences pre and post-treatment as well as differences between

RP and MBRP treatment groups, we will have a liver function panel test performed on a 2mL sample of each participant's blood collected at baseline, 4, 8, 20, and 32 weeks. Liver function panels will be performed by Boulder Community Hospital Reference Lab.

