### **Secondary analyses.**

In the context of the test of the model in Figure 4, we will conduct secondary analyses to test whether there are effects of methylation on network connectivity and of inflammation on BOLD activation. We will also conduct exploratory analyses to determine whether the treatments are differentially effective by gender, age, or race/ethnicity, and we will explore interactions between mechanisms with appropriate Type I error correction. Finally, we will examine the relationship of early changes in drinking behavior (within the first 2 weeks) and neural adaptations in the analysis plan and how the degree of mindfulness uptake relates to neural and clinical outcomes.

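### The Aim 3 mediation model has no term for drinking before week 20, so continued drinking can produce significant marker-to-brain and brain-to-drinking paths without mediation

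*Combined protocol and SAP*

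**What the plan says.** Section IV, Specific Aim 3 - Mediational analyses, sets the order of variables. For the molecular step: "Mediational analyses will utilize the methylation and inflammation data collected at 4 weeks". For the rest: "changes in cue-elicited BOLD activation and network connectivity strength at 8 weeks as the mediators, and drinking outcome data collected at 20 weeks". On inputs: "The exogenous variable in the model is the contrast that compares MBRP to RP". Hypothesis 4 counts as supported if the arm-to-marker, marker-to-brain and brain-to-drinking paths are significant. Model fit is also examined, and a 1-df test asks whether a direct arm-to-drinking path is needed.

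The background gives alcohol a causal role at each step. The Figure 1 caption says: "Chronic alcohol exposure leads to changes in the immune system via TLR4 mediated increases in cytokines and microglial activation". It continues to damage of the executive control networks and to epigenetic change in dopamine genes. For humans the text adds that "acute binge drinking releases LPS which in turn ligates TLR4 and activates the release of cytokines and inflammation".

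Other sections that might bring drinking into the model do not:

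- **Pretest equivalence** adds a baseline variable only where the arms differ after Bonferroni correction.
- **The questionnaire descriptions** name diet, exercise, stress and sleep as controls for inflammation and epigenetic analyses, and prior treatment as a covariate. Drinking is not among them.
- **Secondary analyses** says "we will examine the relationship of early changes in drinking behavior (within the first 2 weeks) and neural adaptations". This is a separate analysis and does not adjust the Aim 3 paths.

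**The concern.** Only the arm-to-marker path is randomised. The other two are observational associations among people who differ in how much they keep drinking. On the protocol's own theory, someone who drinks through treatment would have higher week 4 cytokines, poorer connectivity and more drinking at week 20, even if cytokines did nothing to the brain and the brain measure did nothing to drinking.

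At stake is the claim that MBRP acts through immune and epigenetic targets rather than simply through less drinking. The plan leans on these paths even if the arms do not differ. The Aim 2 analysis section says "Yet it is still important to know whether levels of methylation or inflammation post-treatment have any impact on changes in" neurocognitive outcomes, and calls Aim 3 critical in that case too.

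**Working it through.** **The plan's own figures.** The Aim 3 power section states .71, .83 and .87 for the smallest path at 150, 200 and 226 participants. These agree with each other (noncentrality about .042 per participant, a path of about r = .20). They cannot be rebuilt from d = .30 without the covariance matrix, which is not given. They concern detection of true paths, so nothing below depends on them.

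**Inputs from the protocol.** 180 completers (226 less 20%); arm effect d = .60 on inflammation; arm effect d = .23 on drinking; two-sided alpha .05.

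**Assumed inputs.** Drinking effect r = .2 to .5 on both marker and connectivity; drinking stability .6 between visits; half of the residual connectivity variance is a stable trait. The protocol gives no drinking-marker correlation. Its -.24 to -.55 are cytokine-connectivity correlations in 30 people.

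**Model with no mediation** (T = arm, 0/1; each e is independent standard normal):

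- D4 = .6·D0 − .23·T + .8e; D8 = .6·D4 + .8e
- I4 = −.6·T + r·D4 + √(1−r²)·e
- Connectivity C0 depends on D0 and C1 on drinking at the scan, each with slope −r; the brain mediator is C1 − C0
- D20 = .6·(drinking at the scan) + .8e

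Drinking at the scan is either D4 or D8. Paths are regressions on observed variables, 2,000 trials per setting.

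**Hand check of the brain-to-drinking path**, ignoring the small arm term:

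- Week 4 cause: ρ = −.6 × .4r / √(1 − .2r²). At r = .5, ρ = −.12/.975 = −.123. Then √177 × atanh(.123) = 1.65, and Φ(1.65 − 1.96) = .38.
- Cause through week 8: ρ = −.6 × .64r / √(1 + .28r²). At r = .5, ρ = −.192/1.034 = −.186. The same steps give 2.50 and Φ(.54) = .71.

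The simulation gives .40 and .71.

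**False significance with the planned model:**

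| r | Cause | Marker-to-brain | Brain-to-drinking | Full chain |
|---|---|---|---|---|
| .2 | week 4 | 6% | 11% | 0.8% |
| .3 | week 4 | 9% | 18% | 2.6% |
| .4 | week 4 | 18% | 27% | 7.7% |
| .5 | week 4 | 36% | 40% | 18.8% |
| .2 | week 8 | 4% | 18% | 0.6% |
| .3 | week 8 | 5% | 33% | 2.0% |
| .4 | week 8 | 6% | 55% | 2.8% |
| .5 | week 8 | 5% | 71% | 3.9% |

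The flat marker-to-brain column in the week 8 rows is a cancellation: D4 correlates .6 with both D0 and D8, so the change score removes the shared part. It depends on equal stability.

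**Sensitivity.** Stable-trait shares of .3 and .7 widen the chain to 0.6%–30% and brain-to-drinking to 9%–85%. A second set of assumptions (226 participants, carry-over .50, arm effect on drinking .23 to .45, arm acting on the marker only through drinking) gives a chain of 0.4% to 29%. There it exceeds 5% only with a drinking effect of .5 on the brain and d = .45. With no arm effect on drinking (marker effect .5, brain effect .3), marker-to-brain is still false in 17%.

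**What each adjustment does** (main assumptions):

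- *Baseline drinking and baseline marker only:* chain 1.7% to 64% (week 4 cause) or 1.6% to 33% (week 8). This can be worse than no adjustment, because conditioning on baseline drinking undoes the partial cancellation in the change score.
- *Plus drinking to week 4:* about 5% per path if week 4 drinking is the cause. If drinking continues to the scan, brain-to-drinking stays false in 19% to 81%.
- *Plus drinking up to the scan:* marker-to-brain and brain-to-drinking each about 5%, chain 0.5% or less. Power for the true arm-to-inflammation path is .99 or more.

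**The case against.** **The fit check is a real safeguard.** An omitted common cause leaves marker-drinking covariance that the chain cannot reproduce. With a 3-df test of the observed-variable chain (main assumptions), fit was rejected in 32% to 96% of trials with a week 4 cause and 14% to 56% through week 8. A full false chain with acceptable fit occurred in about 2% or fewer. This stands, with limits: the plan gives no fit threshold and no consequence of poor fit, misfit does not identify its cause, and single paths may still be read. The direct-path test offers little protection. With no mediation it was nonsignificant in 84% to 93% of trials, which the plan would read as consistent with mediation.

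**A reader might infer that most trials would show a false chain.** Rates of 56% and 92% (r = .4 and .5) do arise if connectivity is modelled as a raw level caused by week 4 drinking. The plan specifies changes, so those rates do not describe it.

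**A reader might infer that the missing baseline marker is the main fault.** It is not. The randomised path needs no baseline value to be unbiased, and in the second set of assumptions a baseline marker alone barely moved the chain (0.6% to 27%, against 0.4% to 29%).

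**A reader might extend the mimicry to both routes.** The preliminary data do not support that: DRD2 methylation correlated negatively with severity (AUDIT −0.276, Alcohol Dependence Scale −0.295), while Hypothesis 2 expects MBRP to lower methylation. Drinking could hide that route.

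**Figure 4 cannot be checked.** A path drawn only there would not be seen; the text names one exogenous variable. Breath testing limits drinking at the visit, not over the preceding weeks.

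**Conclusion.** The concern holds as a gap in specification. As written, Aim 3 cannot separate mediation through inflammation and connectivity from the effects of continued drinking, which the protocol itself treats as a cause of both. The documents do not support saying that a false finding is likely. Under the main assumptions the complete chain is falsely significant in roughly 0.5% to 20% of trials, fewer after the fit check. The weaker link is the brain-to-drinking path, falsely significant in about 10% to 70%.

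These figures rest on assumed drinking effects, stability and residual structure, and on observed variables in place of the latent model. The number of participants with blood and imaging is also unknown, because the remote phase collects neither; fewer would lower all the rates.

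**What to change.** **First reconcile the scan time.** The Aim 3 analysis and the heading of the MRI entry in the instrument table say week 8. The MRI and resting-state sections, Follow-up Assessment II and the visit table say week 32, which falls after the week 20 outcome. The brain-to-drinking path has its intended time order only if the scan precedes the outcome.

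**Then add an adjusted model, reported beside the planned one:**

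1. Include baseline drinking and the baseline value of each marker, but not as the only adjustment.
2. Add Timeline Follow Back drinking up to week 4, with paths to the week 4 markers, the brain measures and week 20 drinking. Add drinking from week 4 up to the scan, with paths to the brain measures and week 20 drinking.
3. Claim support for Hypothesis 4 as a mechanism separate from reduced drinking only if the marker-to-brain and brain-to-drinking paths remain in this model.

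**Cost.** Analysis-plan wording and a few paths. Baseline and week 4 blood and the Timeline Follow Back at every assessment are already in the in-person protocol. Its 30-day window covers each of weeks 0–4 and 4–8. It would leave 84 − 30 = 54 days unobserved in each 12-week gap if the scan is at week 32.

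**Downside.** Early drinking is itself affected by treatment and may lie on the causal path, so the adjusted model can be conservative. That is the reason to show both.
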